5.3 Treatment Administration

5.3.1 Acalabrutinib Administration

Acalabrutinib may be administered in either the tablet or capsule formulation.

Acalabrutinib capsule is administered 100 mg BID and taken orally approximately every 12 hours. The capsules should be swallowed intact with water. Acalabrutinib can be taken with or without food. Subjects should not attempt to open capsules or dissolve them in water. If a dose is missed, it can be taken up to 3 hours after the scheduled time with a return to the normal schedule with the next dose. If it has been > 3 hours, the dose should not be taken and the subject should take the next dose at the scheduled time. The missed dose will not be made up and must be returned to the site at the next scheduled visit.

Patients should avoid the concomitant use of strong inhibitors/inducers of CYP3A4 (see Appendix D) for both capsule and table form of acalabrutinib. Proton pump inhibitors or antacids should be avoided while taking acalabrutinib capsule.

The tablet form of Acalabrutinib is administered at the same dosage and frequency as the capsule. Administration of acalabrutinib maleate tablets with acid reducing agents such as proton

pump inhibitors does not impact the absorption; therefore no modification to dosing regimen is necessary.

5.3.2 Lenalidomide Administration

The lenalidomide starting dose will be based on baseline calculated creatinine clearance as follows:

Table 3. Lenalidomide Starting Dose Based on Renal Function at Study Entry

Baseline Calculated Creatinine Clearance (by Cockcroft-Gault)	Starting Lenalidomide Dose
≥ 60 ml/min	15 mg daily on Days 1 - 21 of each 28-day cycle
≥ 30 and < 60 ml/min	5 mg daily on Days 1 - 21 of each 28-day cycle

For patients with normal renal function (creatinine clearance \geq 60 ml/min), the starting dose will be lenalidomide 15 mg daily with escalation to 20 mg if no excess toxicity. For patients with creatinine clearance \geq 30 and $<$ 60 ml/min, the starting dose will be lenalidomide 5 mg daily with escalation to 10 mg if no excess toxicity. The lenalidomide dose may only be increased if the prior treatment cycle was completed without requiring dose modifications, interruptions or delays due to toxicity. Excess toxicity will be defined as grade 3 or 4 non-hematologic toxicity or grade 4 hematologic toxicity (see Section 6.1).

Prophylactic aspirin or low molecular weight heparin are to be given to patients with a high risk of developing DVT/PE or arterial thromboses unless contraindicated. High risk is defined as a history of DVT/PE, a known hypercoagulable state, and/or taking a concomitant medication associated with an increased risk for a thromboembolic event. Patients with diabetes mellitus or coronary artery disease are considered to be at high risk for arterial thromboembolic events.

Prescriptions for lenalidomide must be filled within 7 days. Dosing will be in the morning at approximately the same time each day. Lenalidomide capsules should be swallowed whole, and should not be broken, chewed, or opened. If a dose of lenalidomide is missed, it should be taken as soon as possible on the same day. If it is missed for the entire day, it should not be made up. Patients who take more than the prescribed dose of lenalidomide should be instructed to seek emergency medical care if needed and contact study staff immediately.

Accurate records will be kept of all oral drug administration (including prescribing and dosing). At study entry, patients will receive a Medication diary, and will be instructed on how to use the Medication diary. At monthly visits, the patient will bring the Medication diary along with all bottles of the study medication to the clinic. The Medication diary for the previous month will be reviewed and a new Medication diary will be given to the patient.

5.3.3 Rituximab Administration

Rituximab at standard dose of 375 mg/m² will be administered according to institutional standard. On each rituximab treatment day, patients are to be pre-medicated with diphenhydramine 50 mg IV or PO and acetaminophen 650 mg PO. Diphenhydramine (25 mg) and/or acetaminophen may be repeated if four hours elapse between the administration of the premedication and starting rituximab. Epinephrine for subcutaneous injection, diphenhydramine hydrochloride for IV injection, and any other medications and resuscitation equipment for the emergency management of severe allergic reactions must be available in the room where rituximab infusions are being performed. Where appropriate, rituximab biosimilars, such as Truxima (rituximab-abbs), Ruxience (rituximab-pvvr), Riabni (rituximab-arrx), can be used instead of rituximab.

The initial rate during the first infusion should be 50 mg/hr. The rate may be increased, if tolerated, by 50-mg/hr increments every 30 minutes to a maximum of 400 mg/hr. If administration is well tolerated during the first infusion, the initial rate during subsequent infusions of therapy may be increased to 100 mg/hr. If tolerated, the rate may be increased by 100-mg/hr increments every 30 minutes to a maximum rate of 400 mg/hr. For more information, see the package insert.

On days when acalabrutinib, lenalidomide and rituximab are given, rituximab should be administered after oral medications.

5.3.4 Obinutuzumab Administration

Each dose of obinutuzumab is 1000 mg, administered intravenously, with the exception of the first infusions in Cycle 1, which are administered on Day 1 (100 mg) and Day 2 (900 mg) (Table 4).

Table 4 Obinutuzumab Dosing Schedule

Cycle and Day of Administration		Dose of Obinutuzumab	Rate of Infusion (in the Absence of Infusion Reactions/ Hypersensitivity during Previous Infusions)
Cycle 1	Day 1	100 mg	Administer at 25 mg/hour over 4 hours. Do not increase the infusion rate.
	Day 2	900 mg	Administer at 50 mg/hour if no infusion reaction occurred during the previous infusion. The rate of the infusion can be escalated in increments of 50 mg/hour every 30 minutes to a maximum rate of 400 mg/hour.
	Day 8	1000 mg	If no infusion reaction occurred during the previous infusion and the final infusion rate was 100 mg/hr or faster, infusions can be started at a rate of 100 mg/hour and increased by 100 mg/hour increments every 30 minutes to a maximum of 400 mg/hour.
	Day 15	1000 mg	
Cycles 2–6, Subsequent cycles	Day 1	1000 mg	If no infusion reaction occurred during the previous infusion and the final infusion rate was 100 mg/hr or faster, infusions can be started at a rate of 100 mg/hour and increased by 100 mg/hour increments every 30 minutes to a maximum of 400 mg/hour.
Additional cycles	Every 2 months, starting cycle 8	1000 mg	

If a planned dose of obinutuzumab is missed, administer the missed dose as soon as possible and adjust dosing schedule to maintain the time interval between doses. If appropriate, patients who do not complete the Day 1 Cycle 1 dose may proceed to the Day 2 Cycle 1 dose.

Obinutuzumab should be administered as a slow IV infusion through a dedicated line. IV infusion pumps (e.g., Braun Infusomat® Space) should be used to control the infusion rate of obinutuzumab. Do not administer as an IV push or bolus. After the end of the first infusion, the IV line or central venous catheter should remain in place for \geq 2 hours in order to be able to administer IV drugs if necessary. If no adverse events occur after 2 hours, the IV line may be removed or the central venous catheter may be de-accessed. For subsequent infusions, access (either IV line or central venous catheter) should remain in place for at least 30 minutes from the end of infusion, and if no adverse events occur after 30 minutes, the IV access may be removed. During the maintenance phase, the IV access may be removed at the end of infusion if no adverse events occurred during the infusion.

All obinutuzumab infusions should be administered after premedication with oral acetaminophen (e.g., 650–1000 mg) and an antihistamine, such as diphenhydramine (50–100 mg), 30–60 minutes prior to starting each infusion (unless contraindicated). The use of prophylactic corticosteroids (e.g., prednisolone 100 mg IV or equivalent) is recommended prior to the first dose of obinutuzumab in Cycle 1. Corticosteroids may also be considered for subsequent infusions in

patients who are thought to be at high risk for IRRs, if deemed appropriate by the investigator. In patients who do not experience a Grade ≥ 2 IRR with their previous infusion (i.e., do not receive medication to treat IRR symptoms and do not experience infusion interruption), premedication for subsequent infusions may be omitted at the investigator's discretion.

Patients who are considered to have a high tumor burden and who are considered to be at risk for tumor lysis syndrome (TLS) by the investigator should also receive TLS prophylaxis prior to the initiation of treatment. These patients should be well hydrated. Starting 1–2 days before the first dose of obinutuzumab, it is desirable to maintain a fluid intake of approximately > 3 L/day. These patients should continue to receive repeated prophylaxis with allopurinol and adequate hydration prior to each subsequent infusion, if deemed appropriate by the investigator.

If a patient's previous infusion of obinutuzumab is well tolerated (defined by the absence of a \geq Grade 2 IRR during a final infusion rate of ≥ 100 mg/hr), subsequent infusions will be administered at an initial rate of 100 mg/hr and increased by 100-mg/hr increments at 30-minute intervals, as tolerated, to a maximum rate of 400 mg/hr. If a hypersensitivity reaction or an IRR develops, the infusion should be temporarily interrupted or slowed down and concomitant medication may be administered if deemed appropriate by the investigator. Upon resolution of symptoms, the infusion will resume at one-half the previous rate (the rate being used at the time that the hypersensitivity or IRR developed) and infusion rate escalation may resume at the increments and intervals described. If the previous infusion rate was not well tolerated, as defined, instructions for the first infusion rate will be used. For more information, please see the package insert and the Obinutuzumab Investigator's Brochure.

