7.4.3 Clinical Use

Cycle 1: The recommended dosage of obinutuzumab is 1000 mg administered over Day 1-and Day 2, and on Day 8 and Day 15 of the first 28-day treatment cycle. Two infusion bags should be prepared for the first dose: 100 mg for the first infusion and 900 mg for the second infusion.

Cycles 2-6: The recommended dosage of obinutuzumab is 1000 mg administered on Day 1 for each 28 day treatment cycle.

- Cycle 1 Day 1, 100 mg: Administer at 25 mg/hr over 4 hours. Do not increase the infusion rate.
- Cycle 1 Day 2, 900 mg: If no IRR occurred during the previous infusion, administer at 50 mg/hr. The rate of the infusion can be escalated in increments of 50 mg/hr every 30 minutes to a maximum rate of 400 mg/hr. If the patient experienced an IRR during the previous infusion, start administration at 25 mg/hr. The rate of infusion can be escalated in increments of up to 50 mg/hr every 30 minutes to a maximum rate of 400 mg/hr.

- Cycle 1 Day 8 1000 mg, Day 15 1000 mg: If no IRR occurred during the previous infusion where the final infusion rate was ≥ 100 mg/hr, infusions can be started at a rate of 100 mg/hr and increased by 100 mg/hr increments every 30 minutes to a maximum of 400 mg/hr. If the patient experienced an IRR during the previous infusion administer at 50 mg/hr. The rate of the infusion can be escalated in increments of 50mg/hr every 30 minutes to a maximum rate of 400 mg/hr.
- Cycles 2-6 Day 1 1000 mg: : If no IRR occurred during the previous infusion where the final infusion rate was ≥ 100 mg/hr, infusions can be started at a rate of 100 mg/hr and increased by 100 mg/hr increments every 30 minutes to a maximum of 400 mg/hr. If the patient experienced an IRR during the previous infusion administer at 50 mg/hr. The rate of the infusion can be escalated in increments of 50mg/hr every 30 minutes to a maximum rate of 400 mg/hr.

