7.4.4 Nursing Implications

Premedications are used to reduce the risk of IRRs. For the first infusion of obinutuzumab, corticosteroid premedication is mandatory. Premedication for subsequent infusions and other premedication should be administered as described below. Hypotension, as a symptom of IRR, may occur during obinutuzumab intravenous infusions. Therefore, withholding of antihypertensive treatments should be considered for 12 hours prior to and throughout each obinutuzumab infusion and for the first hour after administration.

- Cycle 1: All patients
 - Intravenous corticosteroid (e.g. 100 mg prednisone, or 20 mg dexamethasone, or 80 mg methylprednisolone) at least 1 hour prior to obinutuzumab infusion.
 - Oral analgesic/anti-pyretic (e.g. 1000 mg acetaminophen/paracetamol) and anti-histaminic drug (e.g. 50 mg diphenhydramine) at least 30 minutes before Obinutuzumab infusion.
- All subsequent infusions:
 - Patients with no IRR during the previous infusion
 - Oral analgesic/anti-pyretic (e.g. 1000 mg acetaminophen/paracetamol) at least 30 minutes before Obinutuzumab infusion.
 - Patients with an IRR (Grade 1 or 2) with the previous infusion
 - Oral analgesic/anti-pyretic (e.g. 1000 mg acetaminophen/paracetamol) and anti-histaminic drug (e.g. 50 mg diphenhydramine) at least 30 minutes before Obinutuzumab infusion.
 - Patients with a Grade 3 IRR with the previous infusion OR Patients with lymphocyte counts $>25 \times 10^9/L$ prior to next treatment
 - Intravenous corticosteroid (e.g. 100 mg prednisone, or 20 mg dexamethasone, or 80 mg methylprednisolone) at least 1 hour prior to obinutuzumab infusion.
 - Oral analgesic/anti-pyretic (e.g. 1000 mg acetaminophen/paracetamol) and anti-histaminic drug (e.g. 50 mg diphenhydramine) at least 30 minutes before obinutuzumab

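### One sentence in 5.3.4 starts obinutuzumab at 100 mg/hr after a Grade 1 infusion reaction, where Table 4 withholds that rate and 7.4.3 directs 50 mg/hr

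*Combined protocol and SAP*

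**What the plan says.** Three places set the starting rate for an obinutuzumab dose according to what happened at the previous infusion.

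- **Section 5.3.4, prose.** An infusion counts as well tolerated if there was no reaction at or above a "Grade 2 IRR during a final infusion rate of" at least 100 mg/hr. In that case "subsequent infusions will be administered at an initial rate of 100 mg/hr and increased by 100-mg/hr increments at 30-minute intervals", up to 400 mg/hr. For the rest: "If the previous infusion rate was not well tolerated, as defined, instructions for the first infusion rate will be used".
- **Section 5.3.4, Table 4.** The rate column applies "in the Absence of Infusion Reactions/ Hypersensitivity during Previous Infusions". For the 1000 mg doses at C1D8, C1D15 and day 1 of cycles 2 to 6, its cells allow a 100 mg/hr start only if the previous infusion was free of any reaction and ended at 100 mg/hr or faster. They give no rate for use after a reaction.
- **Section 7.4.3.** For the same doses, 100 mg/hr is again limited to patients with no IRR. Otherwise: "If the patient experienced an IRR during the previous infusion administer at 50 mg/hr", rising in 50 mg/hr steps every 30 minutes to 400 mg/hr. No grade is named. Section 7.4.4 has a premedication category headed "Patients with an IRR (Grade 1 or 2) with the previous infusion", so Section 7.4 treats Grade 1 as an IRR.

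Section 6.6 tells sites to slow the infusion and treat symptoms for Grade 1 and 2 reactions, but sets no starting rate for the next dose. Section 5.3.4 closes by referring to the package insert and the Investigator's Brochure. It does not say whether 5.3.4 or 7.4.3 governs.

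**The concern.** The prose in 5.3.4 and the rule in 7.4.3 are both directive, and for one type of patient they cannot both be followed. That patient had a Grade 1 IRR at the immediately previous infusion, which nevertheless ended at 100 mg/hr or faster. A site working from the 5.3.4 prose starts the next 1000 mg at 100 mg/hr. A site working from 7.4.3 starts it at 50 mg/hr. A site working from Table 4 learns that 100 mg/hr is not open to this patient, but not what to use instead.

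At stake is consistent handling of patients who have just reacted, in a multi-institution study whose ALO cohort has 10 patients and exists to assess safety and feasibility. Section 7.4.5 notes that severe and life-threatening IRRs have been reported, although most are mild to moderate.

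**Working it through.** The plan gives no infusion duration for a 1000 mg dose, so there is no figure of its own to reproduce. The check has three steps.

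**1. Which patients and visits fall under both rules**

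| Previous infusion | 5.3.4 prose | Table 4 | 7.4.3 |
|---|---|---|---|
| No IRR, final rate at least 100 mg/hr | 100 mg/hr | 100 mg/hr | 100 mg/hr |
| Grade 1 IRR, final rate at least 100 mg/hr | 100 mg/hr | 100 mg/hr not allowed; no rate given | 50 mg/hr |
| Grade 2 IRR | first-infusion instructions | 100 mg/hr not allowed; no rate given | 50 mg/hr |

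The second row is the conflict claimed here. 7.4.3 sets post-reaction rates for C1D8 and C1D15 (2 doses) and day 1 of cycles 2 to 6 (5 doses), so 2 + 5 = 7 scheduled doses lie in the range of both rules. C1D2 is not one of them: C1D1 runs at a fixed 25 mg/hr, so its final rate cannot reach 100 mg/hr. From cycle 8 onward 7.4.3 gives no rates, so no conflict with it arises.

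How wide the second row is depends on how Grade 1 is read. The premedication paragraph of 5.3.4 explains the absence of a Grade 2 or higher IRR as patients who "do not receive medication to treat IRR symptoms and do not experience infusion interruption". If that explanation is carried over to rates, only a reaction managed by slowing alone, without medication, still counts as well tolerated. That is the minimum case. If the CTCAE grade is used, every Grade 1 reaction with a final rate of at least 100 mg/hr is included.

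**2. Whether the final-rate condition can be met after a reaction**

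Section 5.3.4 has the infusion resume at half the rate in use, after which "infusion rate escalation may resume at the increments and intervals described". Take a reaction at the opening 50 mg/hr step of the 900 mg dose on C1D2, and assume that escalation does resume:

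- 25 mg/hr for 0.5 h = 12.5 mg
- 75 mg/hr for 0.5 h = 37.5 mg
- then 125 mg/hr

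The rate passes 100 mg/hr one hour after resumption, with 12.5 + 37.5 = 50 mg given since then. The condition is reachable. One constructed example does not show how often it is reached.

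**3. Size of the difference for an uninterrupted 1000 mg dose**

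Formula: cumulative dose = sum of (rate × 0.5 h) over the steps, then 400 mg/hr for the remainder.

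- *5.3.4 prose:* 50 + 100 + 150 = 300 mg by 1.5 h. The remaining 700 mg takes 700/400 = 1.75 h. Total 3.25 h.
- *7.4.3:* 25 + 50 + 75 + 100 + 125 + 150 + 175 = 700 mg by 3.5 h. The remaining 300 mg takes 300/400 = 0.75 h. Total 4.25 h.

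| Time from start | 5.3.4 prose | 7.4.3 | Ratio |
|---|---|---|---|
| 1 h | 150 mg | 75 mg | 2.00 |
| 2 h | 500 mg | 250 mg | 2.00 |
| 3 h | 900 mg | 525 mg | 1.71 |
| 3.25 h | 1000 mg | 525 + 350 × 0.25 = 612.5 mg | 1.63 |

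Both schedules have the same 400 mg/hr ceiling.

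**The case against.** The best defence is that 5.3 is headed Treatment Administration and 7.4 sits under Pharmaceutical Information, so sites would take 5.3.4 as operative. That is plausible in practice, but no text says so and 7.4.3 is worded as instructions. It also fails inside 5.3.4, because Table 4 there sides with 7.4.3 against the prose. For the same reason, a reader who infers that Section 5.3.4 as a whole prescribes 100 mg/hr after a Grade 1 reaction would be wrong: the outlier is one sentence.

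A second defence is that the affected group may be very small. Section 6.6 calls for treating symptoms even at Grade 1. If that means medication, and the premedication wording is carried over to rates, the patient no longer counts as well tolerated and the 100 mg/hr rule drops out. This narrows the group but does not empty it: 5.3.4 allows a reaction to be handled by slowing, and leaves medication to the investigator.

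Third, the consequence is limited. Escalation under the prose is as tolerated, and any new reaction must be met by slowing or interruption whichever start was used. This stands.

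Four stronger readings are tempting, and the documents do not support them:

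- *The conflict falls mainly at C1D8, because IRRs cluster in the first 1000 mg.* Only a reaction on C1D2 bears on C1D8, and 7.4.5 does not split reactions between days 1 and 2.
- *Seven doses per patient are exposed.* Seven is the number of visits in range. 7.4.5 says most patients have no IRR after the first 1000 mg.
- *The final-rate condition excludes few patients.* The documents give no Grade 1 or re-escalation frequencies.
- *A 100 mg/hr start is a reportable overdose.* The Overdose text in Section 12.2.2 covers rates faster than the protocol specifies, and a site following the 5.3.4 prose is using a specified rate. Sites might classify it differently, but nothing shows that misreporting would follow.

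**Conclusion.** The contradiction is real and confined to one sentence. After a Grade 1 IRR in the immediately previous infusion, with a final rate of at least 100 mg/hr, the 5.3.4 prose directs a start and step size twice those in 7.4.3, and at odds with Table 4. Following the prose gives 150 rather than 75 mg in the first hour and shortens the infusion from 4.25 to 3.25 hours. The conflict with 7.4.3 is limited to C1D8, C1D15 and day 1 of cycles 2 to 6.

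This rests on Section 7.4 counting Grade 1 as an IRR, as 7.4.4 does, and on escalation resuming after a reaction, which 5.3.4 permits but does not require. The timings assume no interruption. The number of affected patients cannot be derived from the documents.

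A reader might infer that the trial's conclusions are at risk. They are not: no endpoint, stopping rule or ALO feasibility criterion uses infusion rate, and the primary endpoint concerns the ALR cohort. The reason to correct the sentence is that it is an operative dosing rule for patients who have just reacted, and the correction is cheap.

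**What to change.** Amend the 5.3.4 sentence to match Table 4 and 7.4.3:

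- The 100 mg/hr start applies only if the previous infusion had no IRR of any grade and a final rate of at least 100 mg/hr.
- After a Grade 1 IRR, the 1000 mg doses at C1D8, C1D15 and day 1 of cycles 2 to 6 start at 50 mg/hr, rising by 50 mg/hr every 30 minutes to a maximum of 400 mg/hr.

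State the Grade 1 case explicitly. If only the definition of well tolerated is tightened, the fallback to first-infusion instructions would capture these patients as well.

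Do not raise the starting rate after Grade 2 or higher reactions as part of this change. If the first-infusion instructions mean C1D1, that rate is 25 mg/hr, and applying the 50 mg/hr rule to everyone would double it for the patients with the worse reactions. The sponsor's clinicians should settle that rate, and the rate after a reaction from cycle 8 onward, as separate decisions. They should preferably do so before the amendment is issued, so that narrowing the sentence leaves no gap.

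The cost is protocol wording, a memo to sites and about 4.25 − 3.25 = 1 hour more per affected infusion. No procedures are added.

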5.4 General Concomitant Medication and Supportive Care Guidelines

5.4.1 Recommended Concomitant Medications/Procedures

Subjects should receive full supportive care, including transfusions of blood and blood products, antibiotics, analgesics, and antiemetics when appropriate.

5.4.1.1 Anticoagulation Consideration

Lenalidomide increases the risk of thrombotic events in patients who are at high risk or with a history of thrombosis, in particular when combined with other drugs known to cause thrombosis. When lenalidomide is combined with other agents such as steroids (e.g. dexamethasone, prednisone), anthracyclines (Doxil, Adriamycin) and erythropoietin the risk of thrombosis is increased. Prophylactic aspirin or low molecular weight heparin are to be given to patients with a high risk of developing DVT/PE or arterial thromboses unless contraindicated. If prophylactic anti-coagulation is used, it should be held for platelet counts $< 50,000/\text{mm}^3$, and then restarted when platelet counts are above this level.

